6.5.6.3 Pharmacokinetic evaluation

6.5.6.3.1 Non-compartmental analysis

The serum anakinra concentration data from full PK sampling will be analyzed by non-compartmental analysis (NCA) using Phoenix WinNonlin. The following PK variables will be derived where applicable:

C_{\max}	Observed maximum serum concentration of anakinra
t_{\max}	Time to reach C_{\max} following dose injection
AUC_{last}	Area under the serum concentration-time curve from time zero to the last quantifiable concentration (C_{last}), calculated by the linear up-log down trapezoidal method
$AUC_{0-24\text{h}}$	Area under the serum concentration-time curve during a dosage interval
V_d/F	Apparent volume of distribution following subcutaneous administration
$t_{1/2}$	Apparent terminal half-life, calculated by $0.693/\lambda_z$
CL/F	Apparent total clearance of drug from serum after subcutaneous administration

The individual serum concentration data, and the actual time for anakinra administration and blood sampling will be used throughout the analyzes.

Samples with serum concentrations below the lower limit of quantitation (LLOQ) at early time-points will be treated as zero. Serum concentrations below the LLOQ appearing in the terminal samples will be omitted from the analysis.

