### 3.3.6 Pharmacokinetic endpoints

The study has the following PK endpoints:

• Anakinra trough plasma concentrations and repeated-dose PK parameters at Week 12.

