### 8.5.7 Non-compartmental pharmacokinetic analysis

The serum anakinra concentration data from full PK sampling will be analyzed by NCA using SAS version 9.4. The following PK variables will be derived where applicable:

Cmax Observed maximum serum concentration of anakinra
 tmax Time to reach Cmax following dose injection
 AUClast Area under the serum concentration-time curve from time zero to the last quantifiable concentration (Clast), calculated by the linear up-log down trapezoidal method
 AUC0-24h,ss Area under the serum concentration-time curve during a dosage interval
 Vd/F Apparent volume of distribution following subcutaneous administration
 λz Terminal slope

 $t^{1/2}$  Apparent terminal half-life, calculated by  $0.693/\lambda z$ 

CL/F Apparent total clearance of drug from serum after subcutaneous

administration

The individual serum concentration data, and the actual time for anakinra administration and blood sampling will be used throughout the analyses. Samples with serum concentrations below the lower limit of quantitation (LLOQ) at early time-points will be treated as zero. Serum concentrations below the LLOQ appearing in the terminal samples will be omitted from the analysis.

Cmax and tmax will be derived directly from observed serum anakinra concentration values. AUClast will be calculated using the linear/log trapezoidal rule.

Extrapolation to 24h will be performed by adding the residual area up to 24h, ( $C_{8h, pred}/\lambda z$ - $C_{24h}$ ,  $_{pred}/\lambda z$ ), where  $\lambda z$  will be determined by linear regression of the log terminal part of the serum concentration versus time curve,  $C_{8h, pred}$  will be the predicted (according to the regression line) concentration at the time of the last sample (8h) and  $C_{24h, pred}$  will be the predicted (according to the regression line) concentration at 24h. CL/F will be calculated as Dose/AUC0-24h,ss and  $V_d$ /F will be calculated as  $\lambda z$  x CL/F.

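### SAP 8.5.7 computes Vd/F by multiplying λz by CL/F; the result is not a volume, and CL/F should be divided by λz.

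*SAP*

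**What the plan says.** SAP 8.5.7 lists the Week 12 non-compartmental parameters and says how each is derived. Four of its statements matter here:

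- Half-life: "Apparent terminal half-life, calculated by" 0.693/λz.
- λz itself "will be determined by linear regression of the log terminal part of the serum concentration versus time curve".
- AUC over the dosing interval: "Extrapolation to 24h will be performed by adding the residual area up to 24h". The residual is the predicted concentration at 8 h divided by λz, minus the predicted concentration at 24 h divided by λz.
- CL/F is dose divided by the steady-state AUC over 24 h.

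The section then closes with the rule for Vd/F: "F will be calculated as $\lambda z$ x CL/F", where the first letter is the F of Vd/F.

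Protocol 6.5.6.3.1 names the same parameter, "Apparent volume of distribution following subcutaneous administration", and gives no formula. It says the data "will be analyzed by non-compartmental analysis (NCA) using Phoenix WinNonlin". The SAP changes the software: "The serum anakinra concentration data from full PK sampling will be analyzed by NCA using SAS version 9.4".

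SAP 3.3.6 makes these parameters part of an endpoint ("Anakinra trough plasma concentrations and repeated-dose PK parameters at Week 12"), and SAP 14 has the calculated values listed.

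**The concern.** A volume of distribution must come out in litres. A rate constant multiplied by a clearance does not. The SAP line is the only place in either document that says how Vd/F is obtained, so a programmer or validator working from the SAP has no other text to check against.

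If the line is coded as it stands, every derived Vd/F is wrong, and wrong in a way that depends on each patient's own elimination rate. The column would look like ordinary PK output but would rank patients incorrectly. A quality check that compares output with the SAP could pass it.

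**Working it through.** Neither document reports a Vd/F value for this trial, so there is no figure to reproduce. The check is on units first and then on size.

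**Units, from SAP 8.5.7 alone**

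- Half-life in hours = 0.693/λz, so λz is in 1/h. The residual-area term agrees: concentration divided by λz is an area only if λz is in 1/h.
- CL/F = dose/AUC = mg ÷ (mg·h/L) = L/h.
- As written: λz × CL/F = (1/h) × (L/h) = L/h².
- Inverted: (CL/F)/λz = (L/h) ÷ (1/h) = L.

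The footnote to Table 2 in protocol 6.2.1 also gives CL/F in L/h and V/F in L.

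**Ratio of the written to the intended quantity**

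(λz × CL/F) ÷ ((CL/F)/λz) = λz².

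This ratio carries units, so it is not a fold error. Three comparisons that do not depend on that are below. The half-lives of 4 h and 6 h are the range that protocol 4.1 quotes for RA patients after subcutaneous dosing, used here only as an illustration.

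- λz at 4 h = 0.693/4 = 0.1733 per h.
- λz at 6 h = 0.693/6 = 0.1155 per h.

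1. *Is the error a constant?* The factors differ by (0.1733/0.1155)² = 2.25. No single rescaling repairs the column.
2. *Is the ranking kept?* Take two patients with equal CL/F. The intended formula gives the 6 h patient 0.1733/0.1155 = 1.50 times the volume of the 4 h patient. The written formula gives 0.1155/0.1733 = 0.67 times, so the order is reversed.
3. *Does the answer depend on the clock?* Going from hours to days multiplies both λz and CL/F by 24. The written product changes by 24 × 24 = 576. The quotient changes by 24/24 = 1, as a volume should.

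**A worked patient**

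Protocol Table 2 gives an AUC of 18776 ng·h/mL for a 50 kg patient on 100 mg. That is 18.776 mg·h/L, so CL/F = 100/18.776 = 5.33 L/h.

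| Half-life | λz (1/h) | Written: λz × CL/F | Intended: (CL/F)/λz |
|---|---|---|---|
| 4 h | 0.1733 | 0.923 L/h² | 30.7 L |
| 6 h | 0.1155 | 0.615 L/h² | 46.1 L |

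The written value falls as the half-life lengthens, while the volume rises. CL/F was taken from the tabulated AUC because the clearance coefficient in the table's footnote does not reproduce that AUC. With the footnote value (0.723 L/h at 50 kg) both columns scale down together, and the three comparisons are unchanged.

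**Reach**

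SAP 4.2 expects at least 12 randomized patients at 2:1, so 12 × 2/3 = 8 on anakinra at that minimum.

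**The case against.** The first defence is that a division sign was lost when the PDF was read. That is unlikely: the line has an explicit multiplication sign, and the other divisions in the section (half-life, residual area, CL/F) kept their slash.

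The stronger objections concern weight, and most of them stand:

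- **The correct value can be recovered.** SAP 8.5.7 derives λz, half-life and CL/F for each patient, and SAP 14 lists the calculated parameters. A reader could divide CL/F by λz, or divide the printed figure by λz². The listing loses no information, but it would still show a wrong number under a volume heading.
- **The harm is conditional.** The documents do not show the program or its checks. That the move from WinNonlin to SAS makes literal coding more likely is an inference. A programmer may well notice the units.
- **Little hangs on it.** Vd/F is one of several parameters derived where applicable. It comes only from Week 12 repeated sampling, which protocol 6.1 limits to pre-selected sites and lets patients decline. It is listed and not tested.
- **The count is uncertain.** Eight is the anakinra share at the stated minimum of 12. The number who reach Week 12 with repeated samples is not given and may be smaller.
- **The right formula does not ensure an accurate volume.** Protocol 4.1 puts the time of peak at about 6 h, and protocol 6.5.6.1.1 ends sampling at 8 h, so λz may rest on very few points after the peak.

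None of this makes the written formula a volume.

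**Conclusion.** The formula is wrong as written. This follows from the SAP's own definitions and needs no outside source. The written rule returns the intended volume multiplied by λz², in L/h². The 2.25-fold spread and the reversed ranking (0.67 in place of 1.50) assume half-lives of 4 h and 6 h, which are RA figures; they do not predict the spread in this trial. The unit error and the 576-fold dependence on the choice of hours or days need no such assumption.

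The severity is minor. Only the individual Vd/F values in the Week 12 PK listing are exposed, and only if the line is coded literally. AUC, CL/F, half-life, trough concentrations, efficacy and safety are not touched.

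**What to change.** Replace the last formula in SAP 8.5.7 with:

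Vd/F = (CL/F)/λz = Dose/(λz × AUC0-24h,ss)

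State that λz is the positive rate constant, that is, minus the slope of the log-concentration regression. The section labels λz as the terminal slope, and the fitted slope of a declining curve is negative.

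Correct the matching line in the SAS program, and confirm that the listed Vd/F is in litres and equals CL/F × half-life/0.693 for each patient.

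The cost is one formula in the SAP and one program line. No new samples, data or analyses are needed.

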# 9 Patient disposition

The number and percentage of patients who were enrolled, randomized, who initiated and who completed or discontinued treatment early (before Week 2 and anytime), and who completed or discontinued the study early (before Week 2 and anytime), together with the reasons for discontinuations, will be presented by treatment group.

The number of patients in the mITT set and in the safety set will be presented.

### 10 Demographics and baseline characteristics

### 10.1 Demographics

Baseline characteristics and demographic data, including age, sex, race, and ethnicity will be presented by descriptive statistics for the mITT set and for the Safety set.

#### 10.2 ECG

A baseline 12-lead ECG will be recorded before the first IMP administration, at the Day 1 visit. The number and percentage of patients with abnormal ECG findings will be presented. Any clinically significant abnormalities are also recorded as medical history, and if judged serious, as a SAE.

# 10.3 Primary Still's disease characteristics

Still's disease characteristics including age at diagnosis, age at symptom onset and disease duration, will be summarized for the mITT and Safety analysis sets.

# **Medical history**

All medical history data will be coded using Medical Dictionary for Regulatory Activities (MedDRA), version 21.1.

General medical history at baseline will be presented by SOC and PT for the mITT and Safety analysis sets.

#### 11 Prior and concomitant medication

All prior and concomitant medication will be coded using the WHO Drug dictionary.

The preferred term grouped by ATC level 4 will be used for presentation and sorted in descending order of frequency in total (both treatment groups together) at the top in the table.

Prior medication, concomitant medication at randomization and onset of new concomitant medication after randomization during the study will be summarized separately for both the mITT set and the Safety set.

### 12 Efficacy analyses

### 12.1 Primary efficacy endpoint

The primary endpoint, ACR30 response at Week 2 with absence of fever attributable to the disease during the 7 days preceding Week 2, will be analyzed using the mITT analysis set and will use no missing data imputation other than that described in 8.2.1. Patients who have discontinued study drug prior to Week 2 will be treated as non-responders in the analysis.

The null and alternative hypotheses with respect to the primary efficacy endpoint are defined as:

 $H_0$ :  $P_{anakinra} = P_{placebo}$  $H_A$ :  $P_{anakinra} \neq P_{placebo}$ 

where P is the proportion of patients with ACR30 response as defined for the primary endpoint. Fisher's exact test will be used to test the hypothesis at the two-sided significance level of  $\alpha$ =0.05. The proportion of patients with ACR30 response in each treatment group and the difference in response rates between anakinra and placebo with the corresponding 95 % exact (Santner-Snell) confidence interval (Santner et al 1980) will be presented.

A patient listing of ACR response and the response for individual components by visit, with information on dose of anakinra, age at onset of disease and glucocorticoid use at inclusion, will be provided.

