6.4.6 Prior and concomitant therapy

Intraarticular, intramuscular and intravenous administration of glucocorticoids are prohibited within 4 weeks prior to randomization and during the study. Other administration of glucocorticoid treatment is allowed as concomitant medication during the study if the patient has had a stable dose for at least 1 week prior to randomization. Maximum dose allowed is 1 mg/kg/day (max 60 mg/day). If the patient is on glucocorticoid treatment, the dose can be tapered starting earliest at the Week 2 visit. The patient must have reached at least ACR50 response with no fever in the preceding 7 days at the visit initiating tapering. A suggested glucocorticoid tapering schedule is provided in Appendix 4. All other glucocorticoid treatment is prohibited during the study except topical and inhaled.

Methotrexate is allowed as concomitant medication during the study if the patient has had a stable dose for at least 8 weeks prior to randomization. The dose should remain stable throughout the study as long as it is well tolerated. If prior treatment with methotrexate, discontinuation is required to be at least 4 weeks prior to randomization.

Initiation of continuous NSAID treatment is prohibited during the study. However on demand treatment is allowed.

Narcotic analgesics are not allowed 24 hours prior any study visit.

Use of the following treatments are not allowed concomitantly with the IMP (wash-out periods before randomization are stated in the exclusion criteria see 6.3.2):

- Intraarticular, intramuscular or intravenous administration of glucocorticoids
- Intravenous immunoglobulins

- Canakinumab or any other IL-1 inhibitor
- Tocilizumab, rituximab or any other immunomodulatory medication
- Etanercept, adalimumab, infliximab, or any other TNF inhibitor (investigational or marketed)
- Dapsone or mycophenolate mofetil, Leflunomide, thalidomide or cyclosporine, 6-Mercaptopurine, azathioprine, cyclophosphamide, chlorambucil, or any other immunosuppressant
- Use of any other investigational drug

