8.2 Definition of study populations

The following analysis sets/populations will be used for the statistical analyses:

ITT population: This population is the primary analysis population and will comprise all randomized patients, grouped according to randomization.

PP population: This population will comprise ITT patients that do not have any major protocol violations potentially influencing efficacy variables up to the Week 2 visit. Patients will be grouped according to treatment actually received and the correct stratification information.

Safety population: This population will comprise all patients who received at least one kit of investigational product and patients will be grouped according to the actual treatment received. Patients randomized to placebo that incorrectly received one kit of anakinra or more will be included in the corresponding anakinra group. Patients randomized to anakinra who incorrectly received only placebo kits will be included in the placebo group.

PK population: This population will comprise patients who received anakinra without any major protocol deviations with respect to administration of investigational product. All patients with at least one PK measurement will be included in the population to present anakinra plasma concentrations. Patients in the repeated dose PK population should not have any major protocol deviations with respect to the repeated dose PK measurements.

The ITT is the primary analysis population for the primary and secondary efficacy endpoints. The PP population will be used as a sensitivity analysis for the primary endpoint, the endpoints supporting the primary objective and the key secondary endpoints. The Safety population will be used for the safety analyses. The PK population will be used for evaluating the PK of anakinra.

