# **6** Sample size determination

Assuming the ACR30 response rate with absence of fever at Week 2 is 65 % in patients receiving anakinra and 25 % in placebo patients, 81 evaluable patients (54 anakinra and 27 placebo) would be required to ensure 90 % power in demonstrating that anakinra improves clinical features of Still's disease using a two-sided test at a 5 % significance level. These assumptions are based on the canakinumab and tocilizumab phase 3 clinical studies in SJIA where 65 to 85 % of active patients and 10 to 25 % of placebo patients responded at two weeks,

as well as the Nordstrom study in AOSD where 50 % of anakinra treated patients were in remission after 4 weeks of treatment (Nordstrom et al 2012).

Since recruitment will be stopped before the planned number of evaluable patients have been included, it is anticipated that at least 12 patients will be randomized and included in the analyses.

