#### 7.4 Protocol deviations

Protocol deviations related to study inclusion or exclusion criteria, conduct of the study, patient management or patient assessment will be reviewed prior to DBL and described in the CSR as appropriate.

Major protocol deviations that will lead to exclusion from the mITT analysis set are the following:

- Patient failed to satisfy major disease-specific entry criteria in accordance with the adapted ILAR or Yamaguchi criteria, as detailed in the CSP.
- Patient did not get any dose of IMP.

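### A patient who stays on study drug but receives added anti-inflammatory therapy before Week 2 can be scored as an ACR30 responder, and no planned efficacy analysis changes that score

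*SAP*

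**What the plan says.** **Scoring.** SAP 12.1: "Patients who have discontinued study drug prior to Week 2 will be treated as non-responders in the analysis". It allows no imputation beyond SAP 8.2.1, which repeats the discontinuation rule, sets a missing ACR component to no change and sets missing fever to fever present. Neither section mentions added or prohibited medication. Protocol 8.3.3 and 8.4.1 have the same discontinuation-only rule.

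**Concomitant therapy.** Protocol 6.4.6 on oral glucocorticoid: "Other administration of glucocorticoid treatment is allowed as concomitant medication during the study if the patient has had a stable dose" for at least a week before randomization. It sets a ceiling, permits tapering from the Week 2 visit at the earliest, and ends by prohibiting all other glucocorticoid except topical and inhaled. For methotrexate the section is explicit about the period after randomization: "The dose should remain stable throughout the study as long as it is well tolerated". A bulleted list then names therapies not allowed with study drug. Nothing there says that using one of them ends study drug or sets non-response.

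**Analysis sets.** Protocol 8.2 defines a per-protocol (PP) set of patients who "do not have any major protocol violations potentially influencing efficacy variables up to the Week 2 visit", for sensitivity analysis. The SAP has only the mITT, Safety and PK sets. SAP 7.4 begins "Major protocol deviations that will lead to exclusion from the mITT analysis set are the following" and lists two reasons: failed disease-specific entry criteria, and no dose of study drug.

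**Other analyses.** The sensitivity analysis in SAP 12.1.1 re-scores discontinuers. The tipping-point display covers missing outcomes and is run only after a significant primary result. SAP 11 summarises new concomitant medication. The patient listing in SAP 12.1 shows glucocorticoid use at inclusion only.

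**The concern.** The protocol expects a patient who needs other treatment to stop study drug and move to standard of care, and stopping before Week 2 is scored as failure. A patient who receives the other treatment without formally stopping is scored on observed data. Two patients with a similar clinical course can therefore be scored in opposite ways, depending on whether discontinuation was recorded.

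Glucocorticoids and the listed drugs can move several parts of the composite: fever, CRP, joint counts and the global scores. Where they do, the response is credited to the randomised arm. With about a dozen patients and an exact test, one such credit can change the primary conclusion. SAP 8.4 makes testing of the key secondary endpoints depend on that conclusion.

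**Working it through.** **Inputs from the documents**
- Rates, SAP 6: "Assuming the ACR30 response rate with absence of fever at Week 2 is 65 % in patients receiving anakinra and 25 % in placebo patients".
- Size, SAP 6: 81 evaluable patients (54 + 27) "would be required to ensure 90 % power in demonstrating that anakinra improves clinical features of Still's disease using a two-sided test" at 5%.
- Test, SAP 12.1: "Fisher's exact test will be used to test the hypothesis at the two-sided significance level of" 0.05.
- Expected size, SAP 4.2: at least 12 patients at 2:1, so 8:4.

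**Inputs not in the documents (assumptions)**
- r: share of would-be non-responders who receive added therapy while on study drug.
- q: share of those who then meet ACR30 without fever.

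**1. The plan's own figure.** For two proportions with k = 2, p1 = 0.25, p2 = 0.65, d = 0.40 and pooled p = (0.25 + 2 × 0.65)/3 = 0.517:

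n = [1.960 × √(1.5 × 0.517 × 0.483) + 1.282 × √(0.1875 + 0.2275/2)]² / 0.16 = 22.6, so 23 placebo and 69 in total.

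The continuity correction, n/4 × [1 + √(1 + 6/(2 × n × 0.40))]², gives 26.2, so 27 placebo and 81 in total. The stated size reproduces. By exact enumeration, Fisher's test at 54:27 has 92.0% power, and 6.7% at 8:4.

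**2. Effect on the expected difference.**
- Placebo: 0.25 + 0.75 × r × q
- Anakinra: 0.65 + 0.35 × r × q

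With the same r in both arms the difference is 0.40 × (1 − r × q). At q = 0.65:

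| r | Difference |
|---|---|
| 5% | 38.7 points |
| 10% | 37.4 points |
| 20% | 34.8 points |

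With unequal r and q = 0.65, the direction depends on which arm gets more added therapy:

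| r placebo | r anakinra | Difference | Fisher power at 54:27 |
|---|---|---|---|
| 30% | 10% | 27.7 points | 60.9% |
| 10% | 10% | 37.4 points | 87.4% |
| 0% | 20% | 44.6 points | 96.7% |

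**3. One patient at 8:4.** Two-sided Fisher p-values:
- 8/8 v 1/4: p = 4/220 = 0.018. One placebo patient credited with a response gives 8/8 v 2/4: p = 6/66 = 0.091.
- 7/8 v 0/4: p = 8/792 = 0.010. One placebo patient credited gives 7/8 v 1/4: p = 33/495 = 0.067.
- In the other direction, if one of the seven anakinra responders owed the response to added therapy, non-response scoring gives 6/8 v 0/4: p = 56/924 = 0.061.

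**4. How often.** Expected number of credited placebo patients at 8:4 is 4 × 0.75 × r × 0.65 = 1.95r. That is 0.10 at r = 5% and 0.39 at r = 20%.

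**The case against.** The case against is substantial, and most of it limits the point.

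- **A reader might infer that raising oral glucocorticoid within the ceiling breaks no rule.** The documents do not support that. The closing prohibition on other glucocorticoid in Protocol 6.4.6 can reasonably be read to cover an increase. The text is ambiguous, and the scoring is the same under either reading.
- **A reader might infer that dropping the PP set removed a full safeguard.** That set could catch only events judged to be major violations, and it was only a sensitivity analysis. The protocol's primary analysis already had the discontinuation-only rule, so the SAP did not weaken the primary scoring.
- **Response is not automatic.** Observed data must meet ACR30 with no disease fever for seven days. A patient treated for fever in the second week already fails.
- **The usual route is handled.** Other treatment is described as following discontinuation, and Protocol 9.4 has deviations assessed for continuation. This probably makes the event uncommon but does not exclude it.
- **Cases may be visible.** Medication summaries and the pre-lock deviation review may reveal them. A raised dose of an existing drug may not appear as new medication, though, and no efficacy result changes.
- **The size rests on assumption.** The 8/8 v 1/4 example is a boundary case. At 65% and 25% its probability is 0.65^8 × 4 × 0.25 × 0.75³, about 1.3%.
- **Observed-data scoring is a recognised strategy.** True, but the plan should choose it explicitly, and elsewhere it uses non-response for departures before Week 2.

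**Conclusion.** The gap is real but narrow. Neither document says how to score a patient who remains on study drug, receives added anti-inflammatory therapy before Week 2 and then meets the response criteria. By default that patient is a responder, and no planned efficacy analysis tests the choice.

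The documents give no event rate. Under the equal-rate assumptions the planned difference loses 1.3 to 5.2 points. The sign is not fixed: excess use on placebo shrinks the difference, and enough excess on anakinra enlarges it. A reader might infer a known bias in one direction, or an effect that nothing in the plan could reveal; neither is supported. What does not depend on the assumed rates is the fragility at 8:4, where one reclassified patient can move the primary test across 0.05. This is a worthwhile, low-cost improvement rather than a fatal flaw.

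**What to change.** Before database lock and unblinding:

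1. In SAP 8.2.1, 12.1 and 12.2, and for the Week 1 fever endpoint in 12.3, add: *Patients who, after first dose and before the relevant assessment, receive systemic or intraarticular glucocorticoid above their baseline dose, or a therapy in the bulleted not-allowed list of protocol 6.4.6, are non-responders at that assessment.* For the Week 1 endpoint this means fever present. Vaccines and the timing of narcotic analgesics do not trigger the rule.
2. Identify these patients blinded from the concomitant medication log, including dose changes of existing drugs.
3. Report observed-data scoring as a sensitivity analysis with the same exact methods.
4. Flag these patients in the SAP 12.1 listing.

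The rule does not reach the three continuous Week 1 endpoints in SAP 12.3. Methotrexate is not named in the bulleted list, so the SAP should say whether an increase counts.

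Separately, the glucocorticoid sentences in Protocol 6.4.6 (stable dose before randomization, ceiling, tapering, closing prohibition) must be reconciled so that it is clear whether an increase before Week 2 is a deviation. No clinical rule is proposed, and patient care is unchanged.

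The cost is SAP wording, a blinded medication review and one extra table. The response rate may fall slightly in either arm, and a patient who might have responded without the added therapy is counted as a failure; the sensitivity analysis shows by how much.
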